8.2.5. Clinical Safety Laboratory Assessments

8.2.5.1. Virus Serology

Blood samples collected at Screening will be analyzed for HIV-1, HIV-2, HbsAg, hepatitis B core antibody (anti-HBc IgG + IgM, if IgG positive), and hepatitis C virus antibody titers.

8.2.5.2. Vaccine Titer

A titer against meningococcal serogroups A, C, W135, and Y will be performed at Screening (Section 1.3). Titer measurements will be used to exclude participants without a confirmed immune response. For participants with a documented vaccine titer indicating sufficient protection within 6 months prior to Screening, the titer does not need to be repeated.

8.2.5.3. Tuberculosis Testing

Serum samples for a QuantiFERON®-TB test will be obtained at Screening as specified in the SoA (Section 1.3).

8.2.6. Pregnancy

No studies of ALXN1820 have been conducted in pregnant women. Pregnant or breastfeeding females are excluded from the clinical study. Participants enrolled in the study, and a spouse or partner, will use a highly effective or acceptable method of contraception. Refer to Section 10.4 for additional details.

Following the last study visit, female participants are required to perform a monthly pregnancy test until at least 5 months after the last dose. For the convenience of the participant, a serum sample will be collected when there is a clinic visit, otherwise, urine test need to be done at home (when there is no clinic visit) and the result is to be reported to the Sponsor within 3 days.

Pregnancy data from female participants and female spouses/partners of male participants will be collected from the signing of the ICF until the outcome of the pregnancy is known, which might occur after the last follow-up visit. Any female participant who becomes pregnant while participating in the study will be discontinued from the study intervention. If a pregnancy is reported, the Investigator must immediately inform Alexion within 24 hours of awareness of the pregnancy and follow the procedures outlined in Section 10.4.

8.2.7. Injection or Infusion Site Evaluation

Injection/infusion of antibodies has been associated with injection/infusion reactions, with onset typically during or shortly after completion of the injection/infusion. For this reason, participants will be carefully observed during each injection/infusion.

Subcutaneous injection/infusion or IV infusion-site evaluations will be performed at the time points specified in the SoA (Section 1.3). Injection/infusion site reactions will not be recorded as AEs unless deemed clinically significant.

8.2.8. Injection/Infusion-associated Reactions

Injection/infusion-associated reactions are defined as systemic AEs (eg, fever, chills, flushing, alterations in heart rate and blood pressure, dyspnea, nausea, vomiting, diarrhea, and generalized skin rashes) occurring during or within 24 hours of the start of IV or SC injection/infusion that are assessed by the Investigator to be related to the study drug.

8.2.9. Vaccine and Antibiotic Prophylaxis

To mitigate the risk of *N. meningitidis* infection associated with complement inhibition, all participants in this study will be administered the following:

1. A MCV4 vaccination at least 56 days prior to dosing of ALXN1820 on Day 1 (if not vaccinated with MCV4 within the last 2 years and 6 months, or if participants have been previously vaccinated but there is not adequate documentation to verify prior vaccination).
2. Two injections of the serogroup B meningococcal vaccine. The first injection must be administered at least 56 days prior to dosing on Day 1, with a booster administered at least 28 days prior to dosing on Day 1, with at least 28 days between the first and second injections.
3. Prophylactic antibiotic treatment, oral penicillin V 500 mg twice daily (equivalent to 1×10^6 units) until complement activity has normalized (as determined by CAP assay). If penicillin is not tolerated, or the participant has a penicillin allergy, second-line antibiotics will be initiated at the discretion of the Investigator.

The first dose of antibiotic will be administered orally on Day -1 in the evening, prior to the Day 1 (dose administration) of study drug. For the outpatient portion of the study, participants will be instructed to take the antibiotic approximately at the same times (twice daily) on each scheduled day. A suitable system (such as text messaging) will be used for daily monitoring of participants' compliance with the antibiotic prophylaxis regimen.

Table 22: Predicted ALXN1820 CAP Activity Inhibition and Duration of Antibiotic Prophylaxis Estimates

Cohort	Planned Dose	Duration of Complete Inhibition of CAP Activity (Days After First Dose)	Time of CAP Activity Return to 80% Baseline (Days After First Dose)	Anticipated Antibiotic Prophylaxis Duration (Days)
1	12.5 mg SC	0	0	22
2	50 mg SC	4	9	29
3	150 mg SC	16	26	43
4	450 mg SC	39	54	57
5	450 mg IV	39	53	57
6	1200 mg SC	67	84	85
7	TBD (≤ 2250 mg SC)			
8 and 9	150 mg SC QW \times 5 in healthy participants and participants of Japanese descent	66 (after the 1 st dose)	83 (after the 1 st dose)	113

Cohort	Planned Dose	Duration of Complete Inhibition of CAP Activity (Days After First Dose)	Time of CAP Activity Return to 80% Baseline (Days After First Dose)	Anticipated Antibiotic Prophylaxis Duration (Days)
10	TBD mg SC QW × 3			113

Abbreviations: CAP = complement alternate pathway; IV = intravenous; QC = once weekly; SC = subcutaneous; TBD = to be determined

Analysis of serum samples to establish actual complement activity will be performed using a CAP assay (Wieslab AP assay). The analysis will take place continuously and the results will be used in an interim PK/PD model to update the predicted duration of CAP inhibition. Results will be used to confirm that complement activity has returned to normal; once confirmed, prophylactic antibiotic treatment can be stopped. Antibiotics will be continued in all participants in a cohort, until complement activity for every participant in the cohort has normalized, in order to preserve blinding. All participants will be closely monitored for signs of infection throughout the study.

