5.1. Inclusion Criteria

Male and female participants are eligible to be included in the study only if all the following criteria apply:

Age

1. Participant must be 18 to 65 years of age inclusive, at the time of signing the informed consent.

Type of Participant and Disease Characteristics

2. Participants who are healthy as determined by medical evaluation with no clinically significant or relevant abnormalities as determined by medical history, physical examination, vital signs, 12-lead ECG, and clinical laboratory evaluation (hematology, biochemistry, coagulation, and urinalysis) that is reasonably likely to interfere with participation in or ability to complete the study, or to potentially confound interpretation of study results, as assessed by the Investigator and Sponsor Medical Monitor.
3. Cohort 9 only: Participants of Japanese descent (defined as those participants whose parents and grandparents are both Japanese and who have spent less than 5 years outside of Japan).

Weight

4. Body weight within 50 – 100 kg (inclusive), and body mass index (BMI) within the range 17 – 32 kg/m², (inclusive).

Sex

5. Contraceptive use by men or women should be consistent with local regulations regarding the methods of contraception for those participating in clinical studies. Female participants of childbearing potential and male participants with female partners of childbearing potential must be willing to follow protocol-specified contraception guidance while on treatment and for at least 5 months after last dose of study drug (described in Section 10.4).

Other Inclusion Criteria

6. Serum albumin above lower limit of the normal range (local laboratory) at Screening.
7. QT interval corrected using the Fridericia's formula (QTcF) \leq 450 msec at Screening and prior to dosing on Day 1.
8. Documented vaccination with MCV4 at least 56 days and not more than 2 years and 6 months prior to dosing. Documentation must include a positive titer to confirm an immune response before study drug administration.
9. Documented vaccination with serogroup B meningococcal vaccine at least 56 days and not more than 2 years and 6 months prior to dosing. For participants not previously

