vaccinated with serogroup B meningococcal vaccine, vaccination at least 56 days prior to dosing on Day 1, with a booster administered at least 28 days prior to dosing on Day 1, with at least 28 days between the first and second injections. For participants vaccinated more than 2 years and 6 months prior to dosing, a booster administered at least 28 days prior to dosing on Day 1.

Informed Consent

10. Capable of giving signed informed consent as described in Section 10.1.3 which includes compliance with the requirements and restrictions listed in the informed consent form (ICF) and in this protocol.

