8. STUDY ASSESSMENTS AND PROCEDURES

Study procedures and their timing are summarized in the SoA (Section 1.3). Protocol waivers or exemptions are not allowed.

Immediate safety concerns should be discussed with Alexion immediately upon occurrence or awareness to determine if the participant should continue or discontinue study intervention.

Adherence to the study design requirements, including those specified in the SoA, is essential and required for study conduct.

All screening evaluations must be completed and reviewed to confirm that potential participants meet all eligibility criteria. The Investigator will maintain a screening log to record details of all participants screened and to confirm eligibility or record reasons for screening failure, as applicable.

Procedures conducted as part of the participant's routine clinical management (eg, blood count) and obtained before signing of the ICF may be utilized for screening or baseline purposes provided the procedures met the protocol-specified criteria and were performed within the time frame defined in the SoA, if consistent with site SOP.

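### Section 8.2.9 item 2 orders two serogroup B injections for every participant, while criterion 9, Section 2.3.1.1 and the Schedule of Activities make them depend on vaccination history or documentation

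*Protocol*

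**What the plan says.** The lead-in to Protocol Section 8.2.9 states that "all participants in this study will be administered the following", and three items follow. Item 1 (MCV4) is limited by history: it applies "if not vaccinated with MCV4 within the last 2 years and 6 months", or where earlier vaccination cannot be verified. Item 2 (serogroup B) has no such limit: "Two injections of the serogroup B meningococcal vaccine. The first injection must be administered at least 56 days prior to dosing on Day 1". It then adds a booster at least 28 days before Day 1, "with at least 28 days between the first and second injections".

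Inclusion criterion 9 in Section 5.1 has three tiers:
- Recent vaccination qualifies as it stands: "Documented vaccination with serogroup B meningococcal vaccine at least 56 days and not more than 2 years and 6 months prior to dosing".
- People never vaccinated against serogroup B need two injections, on the same 56-day and 28-day schedule as item 2.
- Older vaccination needs one injection: "For participants vaccinated more than 2 years and 6 months prior to dosing, a booster administered at least 28 days prior to dosing".

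Section 2.3.1.1 limits serogroup B vaccination to people who have not already had it. Footnote e of Tables 4, 6 and 9 limits it to people without adequate documentation. Neither mentions the single booster for older vaccination.

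Section 8 adds that "Protocol waivers or exemptions are not allowed" and that "All screening evaluations must be completed and reviewed to confirm that potential participants meet all eligibility criteria".

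**The concern.** Item 2 is an operative instruction to sites, and Table 12 names Section 8.2.9 among the places that set out the mitigation of the main identified risk. It reproduces criterion 9's schedule for never-vaccinated people, including the 28-day spacing, but without the words that confine that schedule to them. Because item 1 of the same list has a history condition, its absence from item 2 reads as deliberate.

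A site that follows item 2 literally gives previously vaccinated healthy volunteers, who have no direct benefit from the trial, injections that criterion 9 does not ask for. A site that follows criterion 9 departs from Section 8.2.9 as written, with waivers barred. Either way, the result is avoidable injections or arguments about deviations.

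**Working it through.** The plan gives no figure to reproduce. The check sets the texts side by side and counts the serogroup B injections each requires for the study.

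**Literal reading: item 2 means two injections given for this study, whatever the history.** Surplus = item 2 minus criterion 9.

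| History | Item 2 | Criterion 9 | Surplus |
|---|---|---|---|
| Not previously vaccinated | 2 | 2 | 2 − 2 = 0 |
| Vaccinated more than 2 years 6 months before dosing | 2 | 1 | 2 − 1 = 1 |
| Documented, 56 days to 2 years 6 months before dosing | 2 | 0 | 2 − 0 = 2 |

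The two texts agree only in the first row.

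The literal reading also affects lead time. Item 2 needs a first injection at least 56 days before Day 1. Criterion 9 needs 28 days for older vaccination, a difference of 56 − 28 = 28 days, and no new lead time for recent vaccination. This delays dosing only for someone whose MCV4 vaccination is already in order, since a new MCV4 dose carries its own 56-day lead.

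**Lenient reading: earlier injections count toward item 2's two.**
- One older injection: item 2 leaves 2 − 1 = 1 to give, and criterion 9 asks for 1. Surplus 1 − 1 = 0.
- Two recent documented injections: item 2 leaves 2 − 2 = 0, and criterion 9 asks for 0. Surplus 0.
- One recent documented injection: item 2 leaves 2 − 1 = 1. Criterion 9's first tier asks only for documented vaccination, with no number of injections, so it appears to ask for 0. The texts still differ by 1.

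So the lenient reading removes the surplus in the common cases but not the mismatch. The last case also shows that item 2 is the only text requiring a second injection for someone with a single recent documented dose. The fix should not lose that.

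**Which text stands alone.** Criterion 9 and Section 2.3.1.1 depend on history, and footnote e depends on documentation. Item 2 depends on neither.

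**Total across the study.** This would need the share of participants previously vaccinated and their split between older and recent vaccination. The documents give neither, so no total is computed.

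**The case against.** The strongest reply is that the context settles the meaning. Section 8 says that timing is summarised in the Schedule of Activities and that adherence to it is required, and footnote e there confines study vaccination to people without adequate documentation. Section 6.5.1 allows a booster where one is needed. SAP Section 8.5 will tabulate serogroup B immunisation by whether it came before or after consent, so the analysis plan expects some people to arrive vaccinated. Item 2 sets no upper limit on how long before Day 1 the first injection may be. On this view, earlier injections count and the surplus can be 0.

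Much of this stands. The lenient reading is plausible, and the range must start at 0. It fits poorly, though, with a lead-in that speaks of what all participants will be given, and with the history condition written into item 1 but not item 2. It also leaves the single recent injection unresolved.

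A reader might infer more than the documents support:
- *That someone could be dosed under-vaccinated because of item 2.* Criterion 9 governs entry and all eligibility criteria must be confirmed. That check should also catch a booster missed through footnote e or Section 2.3.1.1.
- *That the two sections cannot both be obeyed.* Criterion 9 is a minimum. A previously vaccinated person given two injections on item 2's schedule can satisfy both.
- *That a definite number of surplus injections will be given.* The share previously vaccinated is not stated, and an assumed share would have no basis in the documents.

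**Conclusion.** The inconsistency is real and lies within the current protocol text. Per person, the literal surplus over criterion 9 is 0 if not previously vaccinated, 1 if vaccinated more than 2 years 6 months ago, and up to 2 with recent documented vaccination. If earlier injections count, it can be 0. These counts rest on criterion 9's first tier requiring no further injection, which is what its wording implies.

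Severity is minor. This is an internal inconsistency in a safety instruction, not a fault of design. Its consequences are possible unneeded injections, a possible delay for some previously vaccinated volunteers, and disputed deviations. The entry minimum, endpoints, sample size and analyses are unaffected.

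**What to change.** Condition Section 8.2.9 item 2 on history and count documented earlier injections:

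- (a) Not previously vaccinated, or no adequate documentation of any serogroup B vaccination: two injections, the first at least 56 days and the booster at least 28 days before Day 1, at least 28 days apart.
- (b) Documented vaccination more than 2 years 6 months before dosing: one booster at least 28 days before Day 1.
- (c) Two documented injections, 56 days to 2 years 6 months before dosing: none.
- (d) Only one documented injection in that window: a second, at least 28 days after the first and at least 28 days before Day 1.

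Simply exempting everyone with recent documented vaccination would be unsafe, because it would remove the only requirement for a second injection in case (d).

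Align criterion 9 on two points. Its older tier does not ask for documentation, so an undocumented older vaccination would otherwise fall under both (a) and criterion 9's single booster. Its recent tier does not ask for a completed two-injection series. Then have footnote e of Tables 4, 6 and 9 and Section 2.3.1.1 refer to criterion 9 for serogroup B, so that the single booster is not overlooked in scheduling.

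The cost is a short wording change carried in a protocol amendment, which under Section 10.1.1 needs IRB/IEC approval before use, and a second injection for participants with one recent documented dose, expected to be few. Assessments, sample size, endpoints and analyses do not change.

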8.2.10. Participant Safety Card

Participants will always also be provided a safety card to carry with them. Risk of meningococcal infection will be explained and discussed with participants during the informed consent process, occurring at the Screening Visit. In order to increase the risk awareness and promote quick disclosure of any potential signs or symptoms of infection experienced by the participants during the course of the study, additional discussion and explanation of the potential risks, signs, and symptoms, as described in the ICF, will take place at specific time points throughout the study as noted in the SoA (Section 1.3).

8.3. Adverse Events and Serious Adverse Events

The definitions of AEs and SAEs can be found in Section 10.3.

All AEs will be reported to the Investigator or qualified designee by the participant (or, when appropriate, by a caregiver, surrogate, or the participant's legally authorized representative).

The Investigator and any qualified designees are responsible for detecting, documenting, and recording events that meet the definition of an AE or SAE and remain responsible for following up AEs that are serious, considered related to the study intervention or study procedures, or that caused the participant to discontinue the study intervention (see Section 7).

Procedures for recording, evaluating, follow-up, and reporting AEs and SAEs are outlined in Section 10.3 (Appendix 3).

8.3.1. Time Period and Frequency for Collecting AE and SAE Information

All AEs and SAEs will be collected from the signing of the ICF until the last follow-up visit.

All SAEs will be recorded and reported to Alexion or the designee immediately and under no circumstance should this exceed 24 hours, as indicated in Section 10.3 (Appendix 3). The Investigator will submit any updated SAE data to Alexion within 24 hours of it being available.

Investigators are not obligated to actively seek AE or SAE data after conclusion of the study participation. However, if the Investigator learns of any SAE, including a death, at any time after a participant has been discharged from the study, and he/she considers the event to be reasonably related to the study intervention or study participation, the Investigator must promptly notify Alexion.

8.3.2. Method of Detecting AEs and SAEs

The method of recording, evaluating, and assessing causality of AE and SAE and the procedures for completing and transmitting SAE reports are provided in Section 10.3.

Care will be taken not to introduce bias when detecting AEs and/or SAEs. Open-ended and non-leading verbal questioning of the participant is the preferred method to inquire about AE occurrences.

8.3.3. Follow-up of AEs and SAEs

After the initial AE/SAE report, the Investigator is required to proactively follow-up on each participant at subsequent visits/contacts. All SAEs will be followed up until resolution, stabilization, the event is otherwise explained, or the participant is lost to follow-up (as defined in Section 7.4). Further information on follow-up procedures is provided in Section 10.3.

8.3.4. Regulatory Reporting Requirements for SAEs

Prompt notification of an SAE by the Investigator to Alexion is essential so that legal obligations and ethical responsibilities towards the safety of participants and the safety of a study intervention under clinical investigation are met.

Alexion has a legal responsibility to notify both the local regulatory authority and other regulatory agencies about the safety of a study intervention under clinical investigation. Alexion will comply with country-specific regulatory requirements relating to safety reporting to the regulatory authority, institutional review boards (IRBs)/IECs, and Investigators.

Suspected unexpected serious adverse reactions (SUSARs) must be reported according to local regulatory requirements and Alexion policy and forwarded to Investigators as necessary.

An Investigator who receives an Investigator safety report describing an SAE or other specific safety information (eg, summary or listing of SAEs) from Alexion will review and then file it along with the IB and will notify the IRB/IEC, if appropriate according to local requirements.

8.4. Treatment of Overdose

For this study, any dose of study intervention greater than that specified in the protocol will be considered an overdose. Any blinded dose greater than that specified in the protocol will be considered a suspected overdose. There is no specific treatment or antidote for overdose.

Overdoses are medication errors that are not considered AEs unless there is an untoward medical occurrence resulting from the overdose.

In the event of an overdose or suspected overdose, the Investigator should:

1. Contact the Medical Monitor immediately.

2. Closely monitor the participant for any AE/SAE.
3. Obtain a plasma sample for PK/PD analysis if requested by the Medical Monitor (determined on a case-by-case basis).

Decisions regarding dose interruptions or modifications will be made by the Investigator in consultation with the Medical Monitor based on the clinical evaluation of the participant.

8.5. Pharmacokinetics

Whole blood samples will be collected for measurement of serum concentrations of ALXN1820 as specified in the SoA (Section 1.3). Additional samples may be collected at additional time points during the study if warranted and agreed upon between the Investigator and Alexion. The total blood volume will not exceed the volume limit for healthy participants (Section 8.2.4). The timing of sampling may be altered during the course of the study, based on newly available data (eg, to obtain data closer to the time of peak plasma concentrations) to ensure appropriate monitoring.

- Instructions for the collection and handling of biological samples will be provided by Alexion. The actual date and time (24-hour clock time) of each sample will be recorded.
- Samples will be used to evaluate the PK of ALXN1820. Samples collected for analyses of ALXN1820 serum concentration may also be used to evaluate safety or efficacy aspects related to concerns arising during or after the study.
- Samples may be used for research to develop methods, assays, prognostics and/or companion diagnostics related to dysregulated complement activity.

Study intervention concentration information that may unblind the study will not be reported to investigative sites or blinded personnel until the study has been unblinded.

